arm. We (47, 48, 93, 109) and others (12, 53, 54, 96) have shown that brachial artery catheterization and intravenous catheterization in the antecubital region of the same arm is safe and well tolerated by adult human subjects. FBF at rest and in response to each vasoactive agent will be measured using venous occlusion plethysmography as previously described by the P.I. (30). Endothelium-dependent vasodilation will be assessed by changes in FBF in response to intra-arterial infusions of the endothelial agonists, acetylcholine and bradykinin. FBF responses to intra-arterial sodium nitroprusside will be used to assess endothelium-independent vasodilation. Acetylcholine will be infused at rates of 4.0, 8.0, 16.0  $\mu\text{g}/100\text{ mL}$  of forearm tissue/min, bradykinin at 12.5, 25, 50  $\text{ng}/100\text{ mL}$  of forearm tissue/min, and sodium nitroprusside at 1.0, 2.0, 4.0  $\mu\text{g}/100\text{ mL}$  forearm tissue/min for 5 min at each dose. To avoid an order effect the sequence in which these agents will be administered will be randomized. To determine the contribution of NO to acetylcholine-mediated vasodilation, the acetylcholine dose-response curves will be repeated in the presence of the endothelial NO synthase inhibitor L-NMMA. After allowing 15 minutes for FBF to return to baseline, L-NMMA will be infused at 5  $\text{mg}/\text{min}$  for 10 minutes intra-arterially. This dose of L-NMMA has been shown to safely and effectively inhibit endogenous NO production in adult humans (94). Bradykinin will not be co-infused with L-NMMA because bradykinin stimulated forearm vasodilation is largely mediated by endothelium-derived hyperpolarizing factor rather than NO (50).

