To assess endothelial t-PA release, following the measurement of baseline FBF and at the end of each dose of bradykinin and sodium nitroprusside, blood will be drawn simultaneously from the brachial artery and antecubital vein of the experimental arm to measure local release of fibrinolytic factors. Bradykinin was selected to stimulate endothelial t-PA release based on its specificity and effectiveness at eliciting local and rapid endothelial t-PA release in adult humans (11). Fibrinolytic determinations in response to sodium nitroprusside are required to establish that any observed differences in local endothelial release of t-PA to bradykinin is not due to increased blood flow related shear stress (12, 53). Net endothelial release or uptake of t-PA and PAI-1 (both antigen and activity levels) at each dose of bradykinin and sodium nitroprusside will be calculated as the product of the arteriovenous concentration gradient and the infused forearm plasma flow (12, 54). Arteriovenous concentration gradients for both t-PA and PAI-1 antigen and activity for each subject (at each time point) will be determined by subtraction of the values measured in simultaneously collected venous and arterial blood samples. Forearm plasma flow will be calculated from FBF and arterial hematocrit corrected for 1% trapped plasma. Thus, net release (or uptake) will be calculated using the following equation (12, 54).

$$\text{Net Release} = (C_V - C_A) \times (\text{FBF} \times [101 - \text{Hematocrit}/100])$$

$(C_V - C_A)$  = arteriovenous concentration gradient;  $C_V$  = venous concentration;  $C_A$  = arterial concentration

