*Intra-Arterial Administration of Vitamin C:* After allowing sufficient time (45 minutes) for FBF to return to baseline following the infusions of acetylcholine + L-NMMA, vitamin C will be infused at a constant rate (12 mg/100 mL tissue/min) for 5 minutes. This vitamin C concentration has been shown to both protect human plasma from free radical-mediated lipid peroxidation (37) and improve endothelium-dependent vasodilation and endothelial t-PA release in conditions associated with oxidative stress (79, 97, 101, 106). Vitamin C infusion will be maintained at the same rate while the bradykinin, sodium nitroprusside and acetylcholine dose-response curves are repeated in the same order as performed earlier. Net endothelial release rates of t-PA and PAI-1 (antigen and activity) will be determined at time 0 and 5 minutes of vitamin C infusion and after each dose of bradykinin and sodium nitroprusside in the presence of vitamin C. A 15-minute washout period will be provided between each dose (106).

*Statistical Analysis for Specific Aims 1 and 2.* For Aims 1 and 2 we will deploy standard linear regression techniques to evaluate whether chronic insufficient sleep is associated with (Aim 1) endothelium-dependent nitric oxide-mediated vasodilation and (Aim 2) vascular endothelium capacity to release tissue-type plasminogen activator. In both scenarios, the continuous vascular measures from Aim 1 and Aim 2 will be modeled as dependent variables in separate linear regression procedures. Independent variables for these models will include the primary variable of interest - insufficient sleep - as well as other important covariates including age, sex, race, BMI, CD4 count, and duration of ART. The primary test of the hypothesis will focus on the parameter estimate for insufficient sleep for both models under Aims 1 and 2.

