*Statistical Analysis for Specific Aim 3.* The outcome variables FBF responses to acetylcholine (in the absence and presence of L-NMMA and vitamin C), bradykinin (in the absence and presence of vitamin C) and sodium nitroprusside (in the absence and presence of vitamin C) as well t-PA and PAI-1 release in response to bradykinin and sodium nitroprusside (both in the absence and presence of vitamin C) will be measured at baseline and after 8 weeks. To accommodate the longitudinal collection these continuous outcomes will be modeled using linear mixed effects methods as implemented SAS (proc mixed; SAS Institute, Inc., Cary NC). Within-individual difference between measures before and after treatment condition ( $d_i$ ) can be modeled as the primary outcome measure using standard linear regression techniques as described under Aims 1 and 2. Potential confounders such as age, sex, race, family history, BMI, nadir CD4 count, baseline CD4 count, duration of ART and HIV-1 RNA prior to ART will be considered. B-spline transformations to allow for a non-linear relationship will be considered for continuous predictors. Based on available data, literature and clinical input from co-investigators, other potential confounders may also be considered. Potential covariates will be identified using a univariate screen with entry criteria of  $p < 0.25$  and non-significant covariates will be excluded in a backward stepwise approach. The primary analysis will be intention to treat, although a secondary as-treated analysis will be conducted as well. Given the design, treatment conditions and assessment protocols, we anticipate the missing data (due to subject dropout) to be at least missing at random (MAR), if not missing completely at random (MCAR). Assuming missing data that are MAR or MCAR, a "complete case analysis" would yield valid inference. However, this approach would come at a cost of reducing statistical efficiency. Therefore, we will also employ Schafer's multivariate normal imputation approach as implemented in SAS v9.3 (SAS Institute Inc.; *proc MI* - MCMC Method and *proc MIANALYZE*). According to a recent simulation study, this multiple imputation approach generally performed well and "generated more reliable information than complete-case analysis" (<http://www.ncbi.nlm.nih.gov/pubmed/20106935>). Results from the complete-case analysis will be compared with that of the multiple imputation analysis to ensure consistency of the regression parameters.

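### The printed net-release equation does not match the definition in words beside it: taken literally, plasma flow is about 100 times blood flow (minor)

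*Combined protocol and SAP*

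**What the plan says.** Under Specific Aims 1 and 2, Study Methods (Experimental Protocol), the plan defines net release or uptake of t-PA and PAI-1 in words as "the product of the arteriovenous concentration gradient and the infused forearm plasma flow". The flow term is then defined: "Forearm plasma flow will be calculated from FBF and arterial hematocrit corrected for 1% trapped plasma".

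The next sentence presents the equation as following from those definitions and as the one to be used:

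Net Release = (Cv − Ca) × (FBF × [101 − Hematocrit/100])

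The unit of hematocrit is not stated, and no hematocrit values are given anywhere. The paragraph on vitamin C asks for more of the same quantities ("Net endothelial release rates of t-PA and PAI-1 (antigen and activity) will be determined at time 0 and 5 minutes of vitamin C infusion", and again after each dose of bradykinin and nitroprusside) and gives no other formula.

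The results are trial outcomes. The Aim 2 dependent variable is "vascular endothelium capacity to release tissue-type plasminogen activator", and the Aim 3 outcomes include "t-PA and PAI-1 release in response to bradykinin and sodium nitroprusside".

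**The concern.** Plasma is a part of blood, so the factor that turns blood flow into plasma flow must lie below 1. As printed it is slightly above 100. The 101 is on the percent scale, while Hematocrit/100 is a fraction.

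If someone coded the equation literally, two things would go wrong:

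- Absolute release rates would be far too large and could not be compared with published values.
- The hematocrit term would become negligible beside 101, so the result would be scaled whole-blood flow rather than plasma flow.

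The missing unit is a separate and quieter risk. Even with the equation repaired, entering hematocrit as a fraction gives wrong values, and they would be wrong by too little to be noticed at once.

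**Working it through.** **Inputs.** The words and the equation come from the Study Methods for Aims 1 and 2. The hematocrit values of 35, 42 and 50% are my assumptions, because the documents give none.

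**Step 1: the factor implied by the words.** The plasma fraction is 1 − Hct/100. Adding 0.01 for trapped plasma gives 1.01 − Hct/100, which equals (101 − Hct)/100. This uses the same 101 that appears in the printed equation.

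**Step 2: compare with the printed factor, hematocrit in percent.**

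| Hct (%) | Printed: 101 − Hct/100 | Implied: (101 − Hct)/100 | Ratio |
|---|---|---|---|
| 35 | 100.65 | 0.66 | 152.5 |
| 42 | 100.58 | 0.59 | 170.5 |
| 50 | 100.50 | 0.51 | 197.1 |

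**Step 3: does a different unit rescue the printed form?** No. With hematocrit as a fraction at 42%, 101 − 0.42/100 = 100.996.

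**Step 4: does another reading of the 1% correction change the picture?** Reducing hematocrit itself by 1% gives 1 − 0.99 × Hct/100, which is 0.6535, 0.5842 and 0.5050. These lie within 0.01 of the implied factors above.

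**Step 5: what happens to the hematocrit correction.** From 35% to 50% the implied factor falls by (0.66 − 0.51)/0.66 = 22.7%. The printed factor falls by (100.65 − 100.50)/100.65 = 0.15%. The printed form is therefore close to a fixed multiple of whole-blood flow, and the correction is lost.

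**Step 6: equation repaired, but hematocrit entered as a fraction.** (101 − 0.35)/100 = 1.0065, (101 − 0.42)/100 = 1.0058 and (101 − 0.50)/100 = 1.0050. Divided by 0.66, 0.59 and 0.51, these are 1.52, 1.70 and 1.97 times the implied values.

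**Step 7: how many values depend on the formula.** Counting baseline once, the first series has 1 + 3 bradykinin doses + 3 nitroprusside doses = 7 paired samples. The vitamin C series has 2 (0 and 5 minutes) + 3 + 3 = 8. That makes 15 sampling points. With four measures (t-PA and PAI-1, antigen and activity), 15 × 4 = 60 release values per vascular visit, of which 30 are t-PA.

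**Step 8: effect on inference, if the printed form were used.** A constant multiplier cancels from p-values, percentage changes and standardized effects. The ratio in Step 2 is not constant, however, because the hematocrit correction disappears. Bias would follow if hematocrit differed between the sleep groups or changed over the 8 weeks. Without any bias, between-subject variance could still shift, and with it a p-value. The documents give no hematocrit data, so no size can be put on either effect.

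**The case against.** The strongest reply is that this is a proofreading matter. The mismatch sits in one equation that reached the reader through PDF conversion, and a flattened fraction bar or a shifted bracket would produce exactly this text. A lost decimal point (1.01 becoming 101) explains it just as simply. The words beside the equation describe the right quantity and the method is referenced. A plasma flow 100 times blood flow is physically impossible and hard to overlook, so literal use is unlikely. The count of 60 can also be made to sound larger than it is: the Aim 2 outcome concerns t-PA only, nitroprusside sampling serves as a control for shear stress, and the Aim 3 list does not name the two samples taken on vitamin C alone.

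Most of this stands. A conversion fault cannot be ruled out, the cause cannot be settled from the text, and there is no evidence of a wrong calculation. It does not remove the point. In the text as supplied, the equation is the operative definition of an outcome, it contradicts the sentences that introduce it, and neither unit of hematocrit reconciles them. Even if the source page proves correct, the supplied text still leaves the unit unstated, and that error would not announce itself.

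**Conclusion.** The concern holds, as a minor one. Confidence is high that the equation and the words disagree in the text supplied; whether the source page has the same fault is open. The printed factor exceeds the implied one by about 150 to 200 times over an assumed hematocrit range of 35–50%. The words, together with the printed 101, identify the intended factor to within 0.01. The consequence is conditional: none if the laboratory already uses the implied form, and wrong absolute release rates without a working hematocrit correction if it follows the print.

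**What to change.** 1. Check the equation against the source page.
2. Print it as Net Release = (Cv − Ca) × {FBF × [(101 − Hematocrit)/100]}.
3. State that hematocrit is entered in percent.
4. Confirm that the calculation sheet uses this form and unit for every release value, including those under vitamin C.

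If the sheet is already right, only the printed equation and the unit need attention. The cost is one bracket, one unit and one check of the sheet.

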*Sample Size Calculations For Specific Aims 1 and 2.* Sample sizes were determined based on data from [name] laboratory and available published results of comparable condition-related (e.g. hypertension, obesity) group differences (<6.5h versus >7h habitual sleep) in acetylcholine-mediated endothelium dependent vasodilation and bradykinin-stimulated endothelial t-PA release (13, 77, 81, 93, 98, 99, 105, 106, 108, 109). Sample sizes were calculated based on 90% power at an alpha level of 0.05. This power value is equivalent to a probability of <0.10 of committing a type-II error. Power calculations yielded sample size of 28 subjects per sleep group based on effect sizes of 0.74. This sample size (N=56; n=28/group) should be sufficient to determine clinically and physiologically significant differences between groups if present. To account for an estimated 20% dropout rate, we will enroll 36 subjects.

**Specific Aim 3: To determine if individualized targeted sleep interventions that increase sleep duration and improve sleep quality improve vascular endothelium-dependent nitric oxide-mediated vasodilation and endothelial tissue-type plasminogen activator release in ART-treated HIV-1-seropositive adults.**

*Experimental Strategy.* Middle-aged and older ART-treated HIV-1-seropositive adults who completed Phase I and habitually sleep less than 6.5 hours/night will be offered to undergo 8 weeks of an individualized targeted sleep intervention and follow-up vascular assessments. *Given the heterogeneity of sleep problems in patients with HIV-1 infection resulting in habitual short nightly sleep duration, a “one size fits all” approach is not appropriate for optimization of sleep health in this population.* Thus, we have assembled a team of sleep and circadian specialists to provide an individualized targeted intervention. After a comprehensive sleep and circadian assessment of each subject, members of the investigative team will meet to create an individualized targeted treatment plan. Expert sleep clinicians will implement the plan and use established procedures to monitor compliance.

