*Sample Size Calculations for Specific Aim 3.* Due to the lack of published data regarding the effects of enhancing sleep duration and sleep quality on vascular

endothelial vasodilator and fibrinolytic function in HIV-1-seropositive adults, sample sizes for the targeted sleep intervention were determined based on data from the P.I.s laboratory in HIV-1 adults and published studies on comparable lifestyle intervention (e.g. exercise) effects on nitric oxide-mediated endothelium-dependent vasodilation and endothelial t-PA release in middle-aged and older adults (30, 93, 109). The average magnitude of change in FBF response to acetylcholine was ~30% and a change in t-PA release of ~35%. Corresponding effect sizes were 0.71-1.25. Sample sizes were calculated based on 80% power at an alpha level of 0.05. A sample size of 23 subjects is required to detect this physiologically meaningful change. To facilitate equal gender distribution a sample size of 24 subjects should be sufficient to show significant changes if present. This sample size also allows for detection of a correlation coefficient of 0.35 with greater than 80% power at an alpha level of 0.05 (95). To account for an estimated ~20% dropout rate from the intervention, we will enroll 30 subjects.

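### With 28 subjects per group and an effect size of 0.74, Aims 1 and 2 have about 78% power (two-sided), not the stated 90%

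*Combined protocol and SAP*

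**What the plan says.** The section Sample Size Calculations For Specific Aims 1 and 2 gives the design inputs in consecutive sentences.

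- Target: "Sample sizes were calculated based on 90% power at an alpha level of 0.05".
- Its meaning for the error rate: "This power value is equivalent to a probability of <0.10 of committing a type-II error".
- Result: "Power calculations yielded sample size of 28 subjects per sleep group based on effect sizes of 0.74".
- Adequacy: "This sample size (N=56; n=28/group) should be sufficient to determine clinically and physiologically significant differences between groups if present".

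The section does not say whether the test is one- or two-sided. It names no formula or software and assumes no variance reduction from covariates.

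The section Statistical Analysis for Specific Aims 1 and 2 plans a linear regression for each vascular outcome, with sleep group as the predictor of interest and six covariates (BMI, ART duration, CD4 count, race, sex and age). On which coefficient is tested, it says: "The primary test of the hypothesis will focus on the parameter estimate for insufficient sleep for both models under Aims 1 and 2".

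The section Sample Size Calculations for Specific Aim 3 uses a different target: "Sample sizes were calculated based on 80% power at an alpha level of 0.05". It quotes effect sizes of 0.71 to 1.25 and arrives at 23 subjects.

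**The concern.** Power, alpha, effect size and group size are tied together, so any three fix the fourth. Here all four are stated, and for a comparison of two independent groups they do not fit. A standardised difference of 0.74 is too small to be detected with 90% power by 28 per group.

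Both Aim 1 (vasodilation) and Aim 2 (t-PA release) rest on this one calculation. A reader is told that a true difference of 0.74 would be missed less than one time in ten. If the real figure is nearer two in nine, a null result is weaker evidence against an effect of short sleep than the plan implies. The vascular protocol involves brachial artery catheterisation, so those who weigh its justification also need a correct power figure.

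**Working it through.** **Inputs, from the Aims 1 and 2 sample-size section.** Standardised difference d = 0.74; alpha = 0.05; n = 28 per group, equal groups; stated power 90%. Sidedness is not given, so both cases are shown.

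**1. Attempt to reproduce 28 per group (normal approximation).**

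n per group = 2(z_alpha + z_power)² / d², with d² = 0.5476.

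- Two-sided, 90%: 2(1.960 + 1.282)² / 0.5476 = 38.4, so 39.
- Two-sided, 80%: 2(1.960 + 0.842)² / 0.5476 = 28.7, so 29.
- One-sided, 90%: 2(1.645 + 1.282)² / 0.5476 = 31.3, so 32.

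Neither 90% calculation gives 28. The nearest match is the two-sided 80% calculation.

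**2. Power at 28 per group (normal approximation).**

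Noncentrality = d√(n/2) = 0.74 × √14 = 2.769.

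- Two-sided: Φ(2.769 − 1.960) = Φ(0.809) = 79.1%.
- One-sided: Φ(2.769 − 1.645) = Φ(1.124) = 86.9%.

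**3. The same with the exact noncentral t.**

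| Per group | Power, two-sided | Power, one-sided |
|---|---|---|
| 28 | 77.6% | 86.2% |
| 30 | 80.5% | 88.2% |
| 32 | – | 90.0% |
| 39 | 89.7% | 94.4% |
| 40 | 90.5% | 94.9% |

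The type II error at 28 per group is 100 − 77.6 = 22.4% two-sided and 100 − 86.2 = 13.8% one-sided, against a stated bound of 10%.

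**4. Effect size that 28 per group can detect (two-sided t).** 90% power: d = 0.88. 80% power: d = 0.76.

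**5. Could covariate adjustment close the gap?** If covariates explain a share R² of the within-group variance and are uncorrelated with sleep group, the effective difference is 0.74/√(1 − R²). Setting this equal to 0.882 gives R² = 1 − (0.74/0.882)² = 0.30. With six covariate degrees of freedom, assumed R² values of 0, 0.1, 0.2 and 0.3 give 77%, 82%, 86% and 90% power. The plan states no R².

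**6. Paired or one-sample reading.** At d = 0.74 and 90% power this needs 22 (two-sided) or 18 (one-sided). It does not give 28, and it does not fit two separate groups.

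**7. The Aim 3 figure, for comparison.** A two-sided paired t-test at d = 0.71, the low end of the quoted range, has 81.0% power with 18 subjects, 88.8% with 22 and 90.2% with 23. So 23 is the smallest number that gives 90% at 0.71, yet the section is labelled 80%.

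**The case against.** The strongest reply has four parts.

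- **Sidedness.** The plan never says two-sided. With a one-sided test the type II error is about 14%, or 1.4 times the stated bound rather than twice. This stands as a qualification: the doubling assumes the conventional two-sided test. The 90% claim fails either way.
- **The planned test is not a plain t-test.** It is an adjusted regression coefficient, each agonist is given at three doses, and the plan does not define the outcome summary to which 0.74 refers. So 77.6% is the power on the simplest reading of the stated inputs, not a certain property of the final analysis. But the plan claims no gain from adjustment. Sleep group is observed rather than randomised, so any correlation between group and covariates would reduce such a gain.
- **Interchanged labels are conjecture.** This is partly right. The documents do not identify the source of the error, Aim 3 names no test for its calculation, and surplus power there does no harm. Even relabelled as 80%, 28 falls just short of the 29 or 30 needed. The pattern is a reason to check, not proof. The paired reading of Aim 3 does have support, since its analysis section models the within-person difference.
- **Enrolment.** The same paragraph ends "To account for an estimated 20% dropout rate, we will enroll 36 subjects". Since 28/0.8 = 35, this looks like a per-group figure, but it does not say so. Read as a total, 18 per group would give only about 58% power two-sided, before dropout. Read as per group with no losses, 36 gives 87.2%, still short of 90% two-sided. This is a separate ambiguity. It does not rescue the stated power, but any restated figure depends on 28 evaluable subjects per group.

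**Conclusion.** The concern holds. The stated effect size, alpha and group size give about 78% power (77.6% by t, 79.1% by normal approximation), not 90%, and the type II error is about 22% rather than below 10%. This assumes a two-sided test of two independent groups, 28 evaluable subjects in each, and no variance reduction from covariates. Under a one-sided test the figures are about 86% and 14%, so the stated values are wrong there too. Nothing elsewhere in the plan corrects them. That the 90% and 80% labels of the two sample-size sections were interchanged is plausible but unproven.

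**What to change.** In the sample-size section for Aims 1 and 2:

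1. State that the test is two-sided, if that is the intention.
2. Replace the 90% claim with one of two true statements, each conditional on 28 evaluable subjects per group: about 78% power for a standardised difference of 0.74, or 90% power for a difference of 0.88.
3. Delete the sentence that puts the type II error below 0.10.
4. Check whether the power labels of this section and the Aim 3 section were interchanged, and correct both as needed. On a paired reading, Aim 3 should say that 23 completers give 90% power at an effect size of 0.71.
5. Say whether the enrolment figure of 36 is per group, so that the restated power rests on a clear number of evaluable subjects.

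This costs wording only. No subjects are added, but the stated power becomes less favourable. If the sponsor wants to keep 90% power at 0.74, about 40 evaluable subjects per group are needed, or 40/0.8 = 50 enrolled per group at the plan's own 20% dropout. If the sponsor instead relies on covariate adjustment, the plan should state the assumed R² (about 0.30 would be needed) and justify it.

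### Aims 1 and 2 sample size: enrolment of 36 cannot yield the 56 completers required ('per group' almost certainly omitted), and 28 per group at an effect size of 0.74 gives about 78% two-sided power, not 90%

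*Combined protocol and SAP*

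**What the plan says.** The paragraph headed Sample Size Calculations For Specific Aims 1 and 2 sets the target: "Sample sizes were calculated based on 90% power at an alpha level of 0.05". It glosses this as "This power value is equivalent to a probability of <0.10 of committing a type-II error". The result is given as "Power calculations yielded sample size of 28 subjects per sleep group based on effect sizes of 0.74", and the paragraph adds: "This sample size (N=56; n=28/group) should be sufficient to determine clinically and physiologically significant differences between groups if present". It ends on enrolment: "To account for an estimated 20% dropout rate, we will enroll 36 subjects".

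It does not say whether the test is one- or two-sided, does not name the test behind the calculation, and gives no standard deviation or raw difference behind 0.74. No other section gives a Phase I enrolment figure.

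The Statistical Analysis for Specific Aims 1 and 2 specifies linear regression of each vascular measure on sleep group and "other important covariates including age, sex, race, BMI, CD4 count, and duration of ART". The test is then defined: "The primary test of the hypothesis will focus on the parameter estimate for insufficient sleep for both models under Aims 1 and 2". The sample size paragraph does not mention any gain in precision from the covariates.

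Two statements elsewhere bear on the enrolment figure. Under Specific Aim 3, Experimental Strategy, the intervention is for "adults who completed Phase I and habitually sleep less than 6.5 hours/night will be offered to undergo 8 weeks". The Sample Size Calculations for Specific Aim 3 plan to enrol 30 such subjects.

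**The concern.** Enrolment cannot be smaller than the number of completers it is meant to deliver, and 36 is smaller than 56. As the only recruitment target given for Phase I, it needs to be usable as written.

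The power statement is a separate matter and remains after the enrolment wording is repaired. An effect size of 0.74 with 28 per group looks like roughly 80% power rather than 90%. If so, the paragraph understates the chance of missing a true difference of the planned size. A null result in Phase I would then be read against a claimed miss rate below 10%, when the stated inputs imply about 22% two-sided. Two of the three aims rest on this paragraph.

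**Working it through.** **Inputs.** From the Aims 1 and 2 sample size paragraph: alpha 0.05, power 0.90, effect size 0.74, 28 per group (56 in total), dropout 20%, enrolment 36. From the Aims 1 and 2 analysis section: six named covariates. Assumptions made here: 0.74 is a standardised difference between two group means (d), groups are equal in size, and both sidedness options are shown.

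**Step 1. Enrolment.** Enrolled = completers / (1 - dropout).
- In total: 56/0.8 = 70. Per group: 28/0.8 = 35.
- Backwards from 36 per group: 36 x 0.8 = 28.8 completers per group, which fits 28.
- Backwards from 36 in total: 28.8 completers altogether, or 14.4 per group, which does not fit.
- Cross-check with Aim 3: 36 split equally gives 18 short sleepers, and 18 cannot supply the 30 to be enrolled from Phase I completers.

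**Step 2. Trying to reproduce 28 per group at 90%.** Normal approximation: n per group = 2(z_alpha + z_power)^2 / d^2, with d^2 = 0.5476.
- Two-sided, 90%: 2(1.960 + 1.282)^2 / 0.5476 = 38.4, so 39.
- One-sided, 90%: 2(1.645 + 1.282)^2 / 0.5476 = 31.3, so 32.
- Two-sided, 80%: 2(1.960 + 0.842)^2 / 0.5476 = 28.7, so 29.

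The noncentral t calculation gives 40, 32 and 30. Neither 90% version returns 28.

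**Step 3. Power at 28 per group.** Noncentrality = d x sqrt(n/2) = 0.74 x sqrt(14) = 2.769, with 54 degrees of freedom.
- Two-sided (critical t 2.005): power 0.776, type-II error 0.224.
- One-sided (critical t 1.674): power 0.862, type-II error 0.138.
- Rounding does not explain the gap: d from 0.735 to 0.745 moves two-sided power only from 0.771 to 0.782.
- The d that gives 90% at 28 per group is about 0.88 two-sided or 0.79 one-sided.

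**Step 4. The planned adjusted test.** Divide the noncentrality by sqrt((1 - R2) x VIF) and remove 6 degrees of freedom. R2 is the share of outcome variance explained by the covariates. VIF is the variance inflation caused by their overlap with sleep group. This takes the adjusted difference to be the same 0.74. The documents give neither R2 nor VIF, so a range is shown (two-sided):
- VIF 1.0: R2 = 0 gives 0.774; 0.10 gives 0.816; 0.20 gives 0.858; 0.30 gives 0.900.
- VIF 1.2 (assumed for illustration): 0.697, 0.742, 0.791 and 0.841 at the same R2 values; R2 = 0.42 gives 0.902.

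Two-sided 90% therefore needs R2 of at least about 0.30, and about 0.42 at a VIF of 1.2. One-sided, it needs about 0.13 and 0.28 respectively.

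**The case against.** The enrolment half can fairly be called a slip of the pen. The paragraph speaks of 28 per group immediately beforehand, 36 x 0.8 returns 28.8, and Aim 3 needs more short sleepers than half of 36. This is accepted. A reader might infer that Phase I will really recruit 36 people and so have 14-15 completers per group and only about 47-50% two-sided power. The documents do not support that reading, because everything around the figure points to 36 per group. The sentence still needs correcting: elsewhere in the paragraph per-group figures are labelled as such, and the parallel Aim 3 sentence gives a total.

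On power, the best objection is that 0.74 is not defined. It covers two outcomes, comes without a standard deviation or a named test, and rests on laboratory data and published studies that are not reproduced. This stands as a limit: the 78% holds only if 0.74 is a two-group standardised difference, which is the natural reading for a comparison of two sleep groups.

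A second objection is that the planned test is covariate-adjusted and may be more powerful than a t-test. It may be, but the plan claims no such gain and gives no R2. Sleep groups are formed by habitual sleep rather than by randomisation, so some overlap with the covariates is plausible and would work the other way. Overlap does not rule out 90%; it raises the R2 required.

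A third is that 36 per group offers a margin. Even with no dropout at all, 36 per group gives 87% two-sided. One-sided it would give 93%, but the plan attributes its 90% to 28 per group, after dropout.

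**Conclusion.** Both errors hold. The enrolment figure is impossible as a total and almost certainly lacks the words 'per group'; on that reading the intended total is 70-72. The power claim is not reproducible from its stated inputs: about 78% two-sided or 86% one-sided, against 90%, with a type-II error of about 0.22 or 0.14 against the stated bound of 0.10. These figures rest on an unadjusted two-sample t-test with equal groups and on reading 0.74 as a standardised mean difference.

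Three stronger conclusions might be drawn, and none is supported. The first is that 78% is the power of the planned regression: that power is unknown, because it depends on an R2 and a covariate overlap that the plan does not state. The second is that the study must be enlarged: the inputs contradict the stated power, but they do not show which of power, effect size or n is the mistaken one. The third is that the power levels of Aims 1-2 and Aim 3 were exchanged. The figure of 28 is near the 29-30 needed for 80% two-sided but does not equal it, and the idea is not needed to establish the error.

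**What to change.** First ask the sponsor two questions: is 36 per sleep group, and which of power, effect size or n was mis-stated? Restating the power before the second answer could put a new error in place of the old one.

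If 28 per group and 0.74 both stand:
- State enrolment as 35-36 per sleep group, 70-72 in total.
- State the sidedness, the test assumed and what 0.74 standardises.
- Restate power as about 78% two-sided (or 86% one-sided), unadjusted, and correct the type-II sentence to about 0.22 (or 0.14).
- Claim a gain from covariates only with a stated and justified R2, allowing for overlap with sleep group. Use a larger effect size (about 0.88 two-sided or 0.79 one-sided for 90%) only if the cited data support it.

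This costs a few sentences and a less favourable stated power; design and sample size stay the same. If the sponsor would rather keep 90% two-sided, unadjusted, at 0.74, the cost is real: 40 completers per group, so 40/0.8 = 50 enrolled per group and 100 in total.
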